## LIST OF ABBREVIATIONS

AE	adverse event
ALT	alanine aminotransferase (also SGPT)
APRI	AST:platelet ratio index
APTT	activated partial thromboplastin time
AST	aspartate aminotransferase (also SGOT)
BPM	beats per minute
CI	confidence interval
CMH	Cochran-Mantel-Haenszel
CSR	clinical study report
DAA	direct acting antiviral
DMC	Data Monitoring Committee
ECG	electrocardiogram
eCRF	electronic case report form
EOT	end of treatment
ESRD	End Stage Renal Disease
FAS	full analysis set
FDC	fixed-dose combination
FU	follow-up
GT	genotype
HCV	hepatitis C virus
HLGT	high level group term
HLT	high level term
HRQoL	health related quality of life
INR	international normalized ratio of prothrombin time
IWRS	interactive web response system
LDV	ledipasvir
LLOQ	lower limit of quantitation
LLT	lower level term
MedDRA	Medical Dictionary for Regulatory Activities
MELD	Model for End-Stage Liver Disease
Peg-IFN	pegylated interferon
PK	pharmacokinetics
PT	preferred term
Q1	first quartile
Q3	third quartile
RNA	ribonucleic acid
SAE	serious adverse event
SAP	statistical analysis plan

SD	standard deviation
SOC	system organ class
SOF	sofosbuvir (Sovaldi®)
SVR	sustained virologic response
SVRx	sustained virologic response x weeks after stopping study drug
TE	treatment-emergent
TFLs	tables, figures, and listings
TND	target not detected
ULN	upper limit of normal
VF	virologic failure
WHO	World Health Organization

## 1. INTRODUCTION

This statistical analysis plan (SAP) describes the statistical analysis methods and data presentations to be used in tables, figures, and listings (TFLs) in the clinical study report (CSR) for Study GS-US-337-4063. This SAP is based on the amended study protocol dated 02 March 2017 and the electronic case report form (eCRF). The SAP will be finalized prior to database finalization. Any changes made after the finalization of the SAP will be documented in the CSR.

### 1.1. Study Objectives

[figure not shown]
The primary objectives of this study are:

- To evaluate the antiviral efficacy of treatment with ledipasvir/sofosbuvir (LDV/SOF) for 8, 12, or 24 weeks in subjects with chronic hepatitis C virus (HCV) infection who are on dialysis for End Stage Renal Disease (ESRD), as measured by the proportion of subjects with sustained viral response 12 weeks after cessation of treatment (SVR12)
- To evaluate the safety and tolerability of each treatment regimen

The secondary objectives of this study are:

- To determine the proportion of subjects who attain SVR at 4 and 24 weeks after cessation of each study treatment regimen (SVR4 and SVR24)
- To evaluate the proportion of subjects with virologic failure
- To evaluate the kinetics of circulating HCV RNA during treatment and after cessation of treatment
- To evaluate the emergence of viral resistance to LDV and SOF during treatment and after cessation of treatment
- To evaluate the steady-state pharmacokinetics of LDV and SOF and its metabolites in subjects who are on dialysis for (ESRD)

The exploratory objectives of this study are:

## 1.2. Study Design

This is a multicenter, open-label Phase 2 study that will evaluate the safety, tolerability, and antiviral efficacy of LDV/SOF in subjects on dialysis for ESRD with genotype 1, 4, 5, or 6 HCV infection.

Approximately 100 subjects with genotype 1, 4, 5, or 6 HCV infection will be enrolled to 1 of 3 groups and will receive treatment with LDV/SOF for 8, 12, or 24 weeks. The treatment group to which subjects are assigned will be determined by genotype, the absence or presence of cirrhosis and whether the subject is treatment naïve or treatment experienced.

Group 1: Treatment naïve genotype 1 subjects without cirrhosis will be treated with LDV/SOF for 8 weeks

Group 2: Treatment experienced genotype 1 subjects and treatment naïve or treatment experienced genotype 4, 5, and 6 subjects without cirrhosis will be treated with LDV/SOF for 12 weeks

Group 3: Subjects with compensated cirrhosis will be treated with LDV/SOF for 24 weeks

The total time to complete all study visits is approximately 52 weeks (42 weeks for those requiring extension of the Screening period):

- 28 days (4 weeks) screening period (or 42 days for extenuating circumstances)
- Up to 24 week treatment period
- Up to 24 week posttreatment period

The schedule of assessments is provided as an appendix to the SAP ([Appendix 1](#)).

## 1.3. Sample Size and Power

With a sample size of 100 subjects, a 2-sided 95% exact confidence interval will extend at the most 20% in length.

## **2. TYPE OF PLANNED ANALYSIS**

### **2.1. DMC Analyses**

An external multidisciplinary Data Monitoring Committee (DMC) will review the progress of the study and perform interim reviews of safety data in order to protect subject welfare and preserve study integrity. The DMC will recommend to the sponsor whether the nature, frequency, and severity of adverse effects associated with study treatment warrant the early termination of the study in the best interests of the participants, whether the study should continue as planned, or whether the study should continue with modifications.

Reviews will be conducted after the first 12 subjects have completed 12 weeks of treatment, or early termination. After the initial meeting, safety reviews will be conducted at approximately 3 month intervals during the trial until the last enrolled subject completes study treatment. These safety reviews will alternate between the following:

- A review by the DMC chair of all SAEs and deaths
- A review of safety data by the DMC meeting as specified in the DMC charter.

The DMC's role and responsibilities and the scope of analysis to be provided to the DMC are provided in a mutually agreed upon charter, which defines the DMC membership, meeting logistics, and meeting frequency.

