- During the conduct of the study, a Data Monitoring Committee (DMC) will evaluate safety data in the study after the first n=12 subjects have completed 8 weeks of treatment, or early termination (ET), and then every 3 months until the last subject enrolled completes treatment with study drugs. Furthermore, the Sponsor and the Investigators will perform ongoing safety reviews throughout the study.

Given the medical need for a well-tolerated, highly effective, RBV-free treatment options for HCV infected subjects with ESRD on dialysis; the benefit/risk assessment of this study favors the conduct of the study.

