8.10. Data Monitoring Committee

An external multidisciplinary data monitoring committee (DMC) will review the progress of the study and perform an interim review of safety data once the first 12 subjects have completed 8 weeks of treatment, or early termination. After the initial meeting, safety reviews will be conducted at approximately 3 month intervals during the trial until the last enrolled subject completes study treatment. These safety reviews will alternate between the following:

- A review by the DMC chair of all SAEs and deaths
- A review of safety data by the DMC meeting as specified in the DMC charter

The DMC will provide recommendation to Gilead on whether the nature, frequency, and severity of adverse effects associated with study treatment warrant the early termination of the study in the best interests of the participants, whether the study should continue as planned, or the study should continue with modifications. The DMC may also provide recommendations as needed regarding study design, conduct, and the need for additional meetings or an alternative meeting schedule. The DMC's specific activities will be defined by a mutually agreed charter, which will define the DMC's membership, conduct and meeting schedule.

While the DMC will be asked to advise Gilead regarding future conduct of the study, including possible early study termination, Gilead retains final decision-making authority on all aspects of the study.

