##### **4.2.2. Adherence to Study Drug**

The presumed total number of tablets administered to a subject will be determined by the data collected on the drug accountability CRF using the following formula:

$$\begin{aligned} \text{Total Number of Doses Administered} = \\ (\sum \text{No. of Tablets Dispensed}) - (\sum \text{No. of Tablets returned}) \end{aligned}$$

The level of adherence to the study drug regimen will be assessed based on the total amount of study drug administered relative to the total amount of study drug prescribed at baseline.

The level of adherence will be expressed in percentage using the following formula:

$$\text{Level of Adherence}(\%) = \left( \frac{\text{Total Amount of Study Drug Administered}}{\text{Total Amount of Study Drug Prescribed at baseline}} \right) \times 100$$

Note: If calculated adherence is greater than 100%, the result will be set to 100%.

In this study, the total amount of LDV/SOF prescribed for 8 weeks would require 56 tablets, for 12 weeks would require 84 tablets, and for 24 weeks would require 168 tablets.

Subjects who prematurely discontinue study drug for lack of efficacy (ie, virologic failure) will have the total amount of study drug prescribed calculated up to the first date when virologic failure criteria were met. For virologic failure confirmed by 2 consecutive measurements, the date of the first measurement will be used. If study drug bottles are dispensed on or after the subject first met virologic failure criteria, these bottles will not be included in the calculation of adherence. If a bottle is dispensed and the bottle is returned empty, then the number of tablets returned will be entered as zero. If a bottle is dispensed but not returned (missing), the number of tablets taken from that bottle will be counted as zero.

Descriptive statistics for the level of adherence (n, mean, SD, median, Q1, Q3, minimum, and maximum) with the number and percentage of subjects belonging to adherence categories (eg, {< 80%, ≥ 80 to < 90%, ≥ 90%}) will be provided by treatment group for the Safety Analysis Set. Categorical displays also will be provided for the number of subjects who are at least 80% adherent to their drug regimen (ie, adherence is ≥ 80% for the study drugs).

No inferential statistics will be provided for duration of exposure and adherence to study drug.

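### SAP 2.1 ties the first DMC safety review to 12 weeks of treatment where the protocol says 8, and Group 1 subjects who finish their 8-week course can never count toward the SAP trigger

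*SAP*

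**What the plan says.** On the first DMC review the two documents read:

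- SAP 2.1: "Reviews will be conducted after the first 12 subjects have completed 12 weeks of treatment, or early termination".
- Protocol 8.10: the interim safety review takes place "once the first 12 subjects have completed 8 weeks of treatment, or early termination".
- Protocol 1.5, in the list of measures that mitigate the study's risks: the DMC evaluates safety data "after the first n=12 subjects have completed 8 weeks of treatment", again with early termination as the alternative.

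On treatment length, SAP 1.2 states "Group 1: Treatment naïve genotype 1 subjects without cirrhosis will be treated with LDV/SOF for 8 weeks". Group 2 subjects "without cirrhosis will be treated with LDV/SOF for 12 weeks", and for the third group the text is "Group 3: Subjects with compensated cirrhosis will be treated with LDV/SOF for 24 weeks". SAP 4.2.2 confirms the short course: "the total amount of LDV/SOF prescribed for 8 weeks would require 56 tablets". SAP Table 3-1 gives the 8-week group no Week 12 on-treatment window.

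SAP 7.7, where a change from the protocol's safety plan would be recorded, records none. Both documents leave the details of DMC operation to a charter. Protocol 8.10 assigns it the meeting schedule. SAP 2.1 assigns it meeting frequency and the scope of what the DMC is shown.

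**The concern.** Two documents that should describe one safeguard give different triggers for it, and the SAP version appears to have been written without the 8-week group in mind.

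The safeguard matters here. Protocol 1.4 reports GS-331007 AUC 1280-2070% higher in end stage renal disease than with normal renal function, which is 13.8 to 21.7 times the normal level. Protocol 1.5 names that exposure, and the limited data on the combination in renal impairment, as the study's risks. It also cites lower red cell counts in non-clinical studies at similar exposure. The early DMC look is one of the mitigations behind its conclusion that benefit and risk favor the study. If the SAP sentence governed the timing, that look would come later than the protocol told sites and ethics committees it would. Under one reading it could not be triggered at all.

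**Working it through.** The trigger is a rule, so there is no calculated figure to reproduce. The check compares the two rules, asks who can satisfy each, and then illustrates the timing.

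**1. Is it the same review?** Both documents use 12 subjects, allow early termination as the alternative, and follow the initial meeting with reviews about every 3 months. Protocol 8.10 and SAP 2.1 both alternate a chair review with a full DMC meeting. Only the treatment length differs (8 against 12 weeks).

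**2. Who can count?** Planned durations are from SAP 1.2.

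| Subject | Protocol rule (8 weeks) | SAP rule (12 weeks) |
|---|---|---|
| Group 1, finishes as planned (8 weeks, 56 tablets) | counts at Week 8 | never counts |
| Group 1, stops early | counts | counts |
| Group 2 (12 weeks) or Group 3 (24 weeks), still treated | counts at Week 8 | counts at Week 12 |
| Group 2 or 3, stops before the trigger week | counts | counts |

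Twelve weeks of daily dosing is 84 tablets and Group 1 is prescribed 56. The second row is the odd one: under the SAP a Group 1 subject counts only by failing to finish.

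**3. If the first 12 means the first 12 enrolled.** One Group 1 subject among them who finishes as planned leaves the condition permanently unmet. With Group 1 share f (assumed), the chance that at least one of the 12 is in Group 1 is 1 − (1 − f)^12:

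- f = 10%: 1 − 0.9^12 = 72%
- f = 20%: 1 − 0.8^12 = 93%
- f = 40%: 1 − 0.6^12 = 99.8%

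**4. If it means the first 12 to qualify.** With no early terminations the SAP rule needs about 12/(1 − f) enrolments instead of 12. With accrual of a subjects per week,

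delay ≈ (12 − 8) + [12/(1 − f) − 12]/a weeks.

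Example at f = 40%, so 12/0.6 = 20 enrolments:

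- 100 subjects over 26 weeks, a = 3.85: 4 + 8/3.85 = 6.1 weeks
- 100 subjects over 52 weeks, a = 1.92: 4 + 8/1.92 = 8.2 weeks

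A simulation agrees (6.0 and 8.1 weeks). It used 3,000 runs per setting, 100 subjects enrolled uniformly, 30% of the non-Group-1 subjects in Group 3, and early termination in 0% or 10% of subjects, spread evenly over planned treatment. All of these settings except the total of 100 are assumptions. Mean delay of the SAP trigger against the protocol trigger, in weeks:

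| Group 1 share | 26-week accrual, no early termination | 26-week, 10% | 52-week, none | 52-week, 10% |
|---|---|---|---|---|
| 0% | 4.0 | 3.7 | 4.0 | 3.7 |
| 20% | 4.7 | 4.2 | 5.5 | 4.9 |
| 40% | 6.0 | 5.0 | 8.1 | 6.7 |
| 60% | 8.6 | 6.5 | 13.1 | 10.0 |
| 80% | 16.1 | 9.6 | 28.2 | 17.7 |

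At an 80% share with no early termination, about 1.4% of runs never reach the trigger and are left out of the mean.

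**5. Are Group 1 completers missing from the later look?** No. In the same runs without early termination, the mean number of Group 1 subjects who had already finished when the SAP trigger was met was 6.1 (26-week accrual) or 4.5 (52-week) at a 20% share, and 14.1 or 11.0 at 40%.

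**The case against.** The strongest reply is that SAP 2.1 may never have set the date of any meeting. Both documents give the schedule to the charter. SAP 1 describes a plan for the displays in the clinical study report that need only be final before the database is, which may be after the first DMC meeting. That SAP 7.7 is silent fits a drafting slip better than a deliberate later look. This stands: the documents do not show that the first review was, or would be, late.

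Three stronger readings are tempting and are not supported.

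- A reader might infer that Group 1 completers are left out of the first review. The sentence sets when the review happens, not whose data are shown, and nothing limits the data to the 12 triggering subjects. Those completers are missing from the count only.
- A reader might take 4 weeks as a guaranteed minimum delay. Early terminations count under both rules. If the deciding subject passes Week 8 and stops at Week 10, the gap is 10 − 8 = 2 weeks.
- A reader might treat the longer delays in the table as forecasts. They depend on an assumed group split, accrual rate and early termination rate.

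It is also fair to say that the DMC is one layer among several. Protocol 1.5 adds routine hematology and continuing sponsor and investigator review, 3.4.1 has individual stopping criteria, and 7.2.4 requires serious adverse events to be reported within 24 hours. These limit the consequence of a late look. They do not reconcile the two triggers or make the SAP condition attainable for Group 1 completers.

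**Conclusion.** The contradiction is certain and rests on the text alone: 12 weeks in SAP 2.1 against 8 weeks in protocol 1.5 and 8.10, with no declared change. It is equally certain that a Group 1 subject who completes the planned course cannot satisfy the SAP wording.

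The effect on timing is conditional. If the charter or the DMC data cut followed the SAP sentence, the first look would come 4 weeks or more late when no early terminations count, and the gap would grow with the Group 1 share. With some early terminations it can be slightly under 4 weeks (3.7 in the simulation with nobody in Group 1). If the first 12 enrolled were meant, the trigger would probably never be met, even at a modest Group 1 share.

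No endpoint, analysis set or estimate is affected. The point still deserves correction, because it concerns the operating rule of a safeguard that the protocol offers as a reason to accept the study's risk. The comparison assumes that the protocol in hand is the amendment dated 02 March 2017 on which SAP 1 says it is based.

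**What to change.** Replace the trigger in SAP 2.1 with that of protocol 8.10, so that the first review takes place "once the first 12 subjects have completed 8 weeks of treatment, or early termination". State whether the 12 are the first enrolled or the first to qualify. Check that the DMC charter carries the same trigger.

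If 12 weeks was intended, amend protocol 1.5 and 8.10, record the change and its reason in SAP 7.7, and say how Group 1 subjects who finish at Week 8 are counted.

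The first route costs one line in the SAP and one look at the charter, and changes no analysis, sample size or data collection. The second needs a protocol amendment.

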### **2.2. Interim Analysis**

#### **2.2.1. Posttreatment Week 4 Analysis**

A posttreatment Week 4 analysis will be conducted for administrative purposes after all subjects complete the posttreatment Week 4 visit or prematurely discontinue from study. All safety and efficacy data through the posttreatment Week 4 visit will be included. The results will be restricted to a limited group of individuals within Gilead. There will be no changes to the study design, study conduct, or the sample size as a result of this administrative analysis.

#### **2.2.2. Posttreatment Week 12 Analysis**

The analysis for the primary efficacy endpoint SVR12 will be conducted when all subjects have completed the posttreatment Week 12 visit or have prematurely discontinued from study. All the safety and efficacy data through the Posttreatment Week 12 visit will be cleaned, finalized and included for the analysis.

### **2.3. Final Analysis**

After all subjects have completed the study, outstanding data queries have been resolved, and the database has been cleaned and finalized, the final analysis of the data will be performed.

### **3. GENERAL CONSIDERATIONS FOR DATA ANALYSES**

Analysis results will be presented using descriptive statistics. For categorical variables, the number and percentage of subjects in each category will be presented; for continuous variables, the number of subjects (n), mean, standard deviation (SD) or standard error (SE), median, first quartile (Q1), third quartile (Q3), minimum, and maximum will be presented.

Data collected in the study will be presented in by-subject listings for all subjects in the Safety Analysis Set, unless otherwise specified. All by-subject listings will be presented by subject identification (ID) number in ascending order, unless otherwise specified.

#### **3.1. Analysis Sets**

Analysis sets define the subjects to be included in an analysis. Analysis sets and their definitions are provided in this section. The number of subjects eligible for each analysis set will be provided. Subjects who were excluded from each analysis set will be summarized or provided in a by-subject listing by genotype.

##### **3.1.1. All Enrolled Analysis Set**

All Enrolled Analysis Set includes all subjects enrolled in the study after screening. Subjects are grouped within the All Enrolled Analysis Set by treatment group to which they were enrolled.

##### **3.1.2. Full Analysis Set**

The Full Analysis Set (FAS) includes subjects who are enrolled into the study and received at least 1 dose of study drug. Subjects are grouped within the FAS by genotype and treatment group to which they were enrolled.

This is the primary analysis set for efficacy analyses.

##### **3.1.3. Safety Analysis Set**

The Safety Analysis Set includes all subjects who received at least 1 dose of study drug. Subjects are grouped within the Safety Analysis Set according to the treatment they actually received.

This is the primary analysis set for safety analyses.

##### **3.1.4. Pharmacokinetic (PK) Analysis Set**

The PK Analysis Set includes all subjects who took at least 1 dose of the study drug and have at least 1 nonmissing postdose concentration value for the corresponding analyte in plasma. The analytes of interest may include LDV and SOF (and its metabolites GS-566500 and GS-331007).

###### **3.1.4.1. Intensive PK Substudy Analysis Set**

CCI

CCI

3.1.4.2.

CCI

CCI

### **3.2. Subject Grouping**

For analyses based on the All Enrolled Analysis Set, FAS, or demographic and baseline characteristics tables, subjects will be grouped according to the HCV genotype and treatment group. Unless otherwise specified, groups by genotype including GT1a, GT1b, GT1 Other, GT1 total, GT4, GT5, and GT6, Indeterminate, and Total.

For analyses based on the Safety Analysis Set, subjects will be grouped according to the actual treatment received. The actual treatment received is defined as the enrolled treatment except for subjects who received treatment that differs from the enrolled treatment for the entire treatment duration. In this case, the actual treatment received is defined as the treatment received for the entire treatment duration.

### **3.3. Examination of Subject Subsets**

Subject subsets within each genotype will also be explored by baseline characteristics for the primary efficacy endpoint, SVR12. The baseline characteristics include the following:

- age (< 65 years,  $\geq$  65 years)
- sex (male, female)
- cirrhosis (presence, absence)
- prior HCV treatment experience (treatment naive, treatment experienced)
- prior HCV treatment for treatment experienced subjects [DAA Naive (Peg-IFN + RBV, Other)]
- HCV genotype
- baseline HCV RNA (< 800,000 IU/mL,  $\geq$  800,000 IU/mL)
- baseline body mass index (BMI) (< 30 kg/m^2,  $\geq$  30 kg/m^2)
- baseline alanine aminotransferase (ALT) ( $\leq$  1.5  $\times$  upper limit of normal (ULN),  $>$  1.5  $\times$  ULN)

- IL28B (CC, non-CC; with non-CC further broken down to CT, TT)
- type of current dialysis (Hemodialysis, Peritoneal Dialysis)
- adherence to study regimen (< 80%, ≥ 80%)

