3.3. Duration of Treatment

Approximately 100 subjects will be enrolled to one of 3 groups and will receive treatment with LDV/SOF for 8, 12, or 24 weeks. The treatment group to which subjects are assigned will be determined by genotype, the absence or presence of cirrhosis and whether the subject is treatment naïve or treatment experienced.

Group 1: Treatment naïve genotype 1 subjects without cirrhosis will be treated with LDV/SOF for 8 weeks

Group 2: Treatment experienced genotype 1 subjects and treatment naïve or treatment experienced genotype 4, 5, and 6 subjects without cirrhosis will be treated with LDV/SOF for 12 weeks

Group 3: Subjects with compensated cirrhosis will be treated with LDV/SOF for 24 weeks

The total time to complete all study visits is up to a maximum of 52 weeks depending on the treatment duration (54 weeks for those requiring an extension of the screening period):

- 28 days (4 weeks) screening period (or 42 days for extenuating circumstances)
- 8, 12, or 24 week study treatment period
- 24 week posttreatment period

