#### 6.1.3. Subgroup Analysis of the Primary Efficacy Endpoint

The point estimates and 95% exact CIs of the SVR12 rates will be displayed by genotype for subgroups outlined in Section [3.3](#).

SVR12 rates will be summarized by categories of early viral response to explore possible early on-treatment predictors of SVR12. The relationship between SVR12 and study drug interruption may also be explored. A forest plot will graphically present estimates and 95% CIs in SVR12 rates for each of the subgroups.

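### The SVR12 rows for cirrhosis (every genotype) and prior treatment (GT1 and Total) mix the patient factor with treatment duration, and SAP 3.3 and 6.1.3 neither separate nor flag this

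*SAP*

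**What the plan says.** Duration is assigned, not randomised. SAP 1.2 makes the treatment group "determined by genotype, the absence or presence of cirrhosis and whether the subject is treatment" naive or experienced, and Protocol 3.3 gives the same rule. Treatment-naive "genotype 1 subjects without cirrhosis will be treated with LDV/SOF for 8 weeks" (Group 1). Group 2 takes treatment-experienced genotype 1 subjects, and naive or "treatment experienced genotype 4, 5, and 6 subjects without cirrhosis will be treated with LDV/SOF for 12 weeks". For Group 3, "Subjects with compensated cirrhosis will be treated with LDV/SOF for 24 weeks", whatever their genotype or treatment history.

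SAP 3.3 then states: "Subject subsets within each genotype will also be explored by baseline characteristics for the primary efficacy endpoint, SVR12". Cirrhosis status and prior HCV treatment experience are two entries in that list, alongside age, sex, BMI and others. SAP 6.1.3 displays SVR12 rates and exact 95% CIs by genotype for these subsets and adds: "A forest plot will graphically present estimates and 95% CIs in SVR12 rates for each of the subgroups". Neither section names treatment group or duration as a stratum, and neither notes that two of the listed factors decide duration.

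**The concern.** A subgroup row puts two levels of a factor side by side so that their rates can be compared. That comparison is informative about the factor only if the levels do not also differ systematically in treatment. Here some of them do, by design. A similar SVR12 rate with and without cirrhosis could mean that cirrhosis matters little, or that a cirrhosis deficit was offset by longer treatment. The row cannot tell these apart, and a larger sample would not help.

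This has some practical weight. Protocol 1.4 ties each duration to cirrhosis and treatment history, and Protocol 1.5 expects the data to support dosing recommendations. Readers will want the SVR12 rate at a known duration in a known type of patient.

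**Working it through.** The plan gives no figure on this point. Its only related number is the precision statement in SAP 1.3, that the exact 95% CI is at most 20% long with 100 subjects. Clopper-Pearson limits at 50/100 are 39.83% to 60.17%, a length of 20.34 points, which rounds to the stated 20%. It has no bearing on what follows.

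**Step 1: assignment map** (SAP 1.2, Protocol 3.3), in weeks.

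| Genotype | No cirrhosis, naive | No cirrhosis, experienced | Cirrhosis, naive | Cirrhosis, experienced |
|---|---|---|---|---|
| 1 (including subtypes) | 8 | 12 | 24 | 24 |
| 4, 5, 6 | 12 | 12 | 24 | 24 |

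**Step 2: read the two rows off the map.**

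- Cirrhosis, every genotype: presence is always 24 weeks and absence never is. Confounding is complete.
- Prior treatment, GT1: naive pools 8 and 24 weeks; experienced pools 12 and 24. Among subjects without cirrhosis the factor and the duration coincide exactly (8 versus 12). Among those with cirrhosis both levels receive 24.
- Prior treatment, GT4, GT5 and GT6: both levels follow the same rule (12 or 24 by cirrhosis alone), so prior treatment does not set duration. Durations could differ only through a different cirrhosis mix.
- Prior treatment, Total column: naive pools 8, 12 and 24 weeks; experienced pools 12 and 24. Confounded through the GT1 subjects.

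**Step 3: what a confounded row can show.** The documents give no group sizes, SVR12 rates or effect sizes, so the ranges below are assumptions.

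*Cirrhosis row.* Let cirrhosis lower SVR12 by d points, and let 24 weeks raise it by g points relative to the shorter durations. Then

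absent minus present = d - g.

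With d and g each from 0 to 15:

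- d = 15, g = 0 gives +15
- d = 10, g = 10 gives 0
- d = 0, g = 15 gives -15

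Every pair with d = g shows no difference.

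*GT1 prior-treatment row.* Let p be the deficit in experienced subjects, h the gain from 12 over 8 weeks, and s the share with cirrhosis, taken as equal in both levels. Then

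naive minus experienced = p - (1 - s)h.

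With p and h each from 0 to 10 and s from 0 to 40%:

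- s = 0, p = 0, h = 10 gives -10
- s = 20%, p = 5, h = 5 gives 5 - 0.8 x 5 = +1
- s = 40%, p = 10, h = 10 gives 10 - 0.6 x 10 = +4
- p = 10, h = 0 gives +10 for any s

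In both rows one observed difference fits many combinations of factor effect and duration effect.

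**The case against.** The strongest reply is SAP 3.2, which says that FAS analyses are grouped by genotype and treatment group. If that governs 6.1.3, every row sits at one duration and the confounding disappears. But 3.3 and 6.1.3 are the specific sections and name genotype only, and the groups that 3.2 spells out are genotypes and a total. A two-level cirrhosis row is also impossible within treatment group: Groups 1 and 2 contain no subjects with cirrhosis and Group 3 contains only such subjects. As written, the row can be filled only by pooling groups. At best the layout is ambiguous.

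The second reply is that SAP 3 calls the analyses descriptive and SAP 3.3 calls the subsets exploratory. No difference, interaction test or prognostic claim is planned, and the rate in subjects with cirrhosis on their assigned regimen is a legitimate quantity. All of that stands, and it limits the weight of the point.

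It also rules out several stronger readings that a reader might infer:

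- That prior treatment sets duration throughout. It does so only in genotype 1 without cirrhosis.
- That the affected rows simply compare regimens. Factor and duration move together, so the rows isolate neither.
- That a higher rate with cirrhosis than without would be produced by duration alone. The documents give no rates from which to say so.
- That the rows will be misread. That is a prediction about readers, not a statement in the plan.
- That every other subgroup factor must be split by duration. With about 100 subjects already divided by genotype, that would leave many sparse cells.

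**Conclusion.** The point holds within limits. The cirrhosis row is fully confounded with 24 versus 8 or 12 weeks in every genotype. The prior-treatment row is fully confounded with 8 versus 12 weeks among GT1 subjects without cirrhosis, and so partly in the GT1 and Total columns. It is not confounded by assignment in GT4, GT5 or GT6, or among subjects with cirrhosis.

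This follows from the assignment rule alone and needs no assumed rates. The spans of -15 to +15 and -10 to +10 points only illustrate it under the assumed effects. The conclusion rests on reading 6.1.3 as written, by genotype without a treatment-group split.

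The consequence is confined to the interpretation of a descriptive display. The primary SVR12 estimate is unaffected, and which breakdown is primary is a separate matter. Correcting the rows is a cheap improvement worth making.

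**What to change.** In SAP 6.1.3 and its forest plot, show these two factors within treatment group by reporting n/N and the exact 95% CI for the six design cells:

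- GT1 naive without cirrhosis, 8 weeks
- GT1 experienced without cirrhosis, 12 weeks
- GT4-6 without cirrhosis, naive, 12 weeks
- GT4-6 without cirrhosis, experienced, 12 weeks
- cirrhosis, naive, 24 weeks
- cirrhosis, experienced, 24 weeks

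Adjust SAP 3.3 to match. If the by-genotype rows are also kept, footnote the cirrhosis row, and the prior-treatment row in the GT1 and Total columns, to say that factor and duration cannot be separated. The other subgroup factors can stay as they are.

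The cost is SAP wording and relabelled table and figure rows; no new data are needed. The cells for GT4-6 and for cirrhosis pool genotypes, which departs from the within-genotype layout of 3.3 and should be stated. Some cells may be small with wide intervals: if a cell held 10 subjects, all responding, the exact CI would be 69.2% to 100%; with 19 of 20 responding, 75.1% to 99.9%.
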